All research will be conducted in line with LSBU ethics panel code of conduct for research involving human participants and the British Psychological Society's ethical guidelines. These guidelines include principles of holding participants rights and dignity, anonymity, and freedom to choose to participate or not. Research will also be conducted and reviewed the way which makes it compliant with GDPR (or replacement legislation). Each strand of the research presents a number of particular ethical risks.

Work Package 1:

New data analysis sample: The key ethical risk here is that participants will be asked to recall experiences which occurred over lockdown, which may be upsetting for people. We will mitigate this by fully informing participants of the content of the study in advance.

Social network analysis: The key ethical consideration for this strand of the research is around use of data without participants' explicit consent. Our initial PPIE work has indicated

that such a use would be considered reasonable, data will be anonymised at source and only the source, target and length of interaction will be recorded. We will continue to engage with our PPIE group as this work develops. This issue is also more fully explored in ethical considerations for Work Package 2 (see next section).

Work Package 2:

Qualitative component 1: Participant observation of Facebook interactions analysed using discourse analysis: The key ethical consideration here is the detailed analysis of Facebook postings without participants' explicit consent. LSBU code of practice for human research recognises the need for consent in such studies, but also recognises the principle of fair processing and the need for judgement about the extent the use has the potential to cause distress (LSBU Code of Practice for Human Research, 2020, sections 2.1 and 2.2). Feedback from our PPIE work on this issue confirms that this would be reasonable if the data were anonymised. Feedback also suggested that, although the Facebook group is technically a closed group, it was described as a 'semi-public' space because there are 38,000 members. Furthermore, the only reason that the group is closed is based upon the geographical catchment area. Permission from the site owners/moderators will be obtained.

Qualitative component 2: semi-structured interviews: The key ethical risk here is that participants will be asked to recall experiences which occurred over lockdown, which may be upsetting for people. We will mitigate this by fully informing participants of the content of the study in advance and providing support and debriefing if necessary during the interview.

Assessment and management of risk

Table 3: Risk register

Key risk	Likelihood	Impact on participants	Impact on project	Mitigation
COVID19 interferes with staff availability (research team + stakeholders)	Moderate	N/A	Moderate	Depth of team, clear project planning to facilitate handover, lines of alternative communication established, agreement to support the evaluation through a Memorandum of Collaborations between LSBU and ECC
Failure to recruit to quantitative strand	Moderate	N/A	High	Guidance from PPIE in planning stage Leverage market research panel resources
Data not available from partners	Low	N/A	Moderate	Agreement with partners on data, ongoing stakeholder involvement Agreement in place to support the evaluation through a Memorandum of Collaborations between LSBU and ECC

Amendments

Significant amendments to the protocol will be discussed in advance with the PHIRST London Central Executive Committee and PH Essex. Should these discussions suggest a need for consultation with the NIHR, this will be co-ordinated by PHIRST London.

Peer review

This protocol will receive a proportionate review by PHIRST London and the NIHR.

Patient & Public Involvement and Engagement

The workshops that informed this design were attended by three Essex community members who have been involved in the development and implementation of ECAS. As these members also received a financial recompense from ECC for their involvement, we extended our PPIE strategy to establish a PPIE Advisory Panel made up of ECAS users and Community Admins involved on a voluntary basis. The project aims to have in place a PPIE Advisory Panel of five members in total. Recruitment was undertaken through advertising on the Facebook page and targeted recruitment for Admin. Three panel members have been active so far and further recruitment is ongoing.

The first introductory meeting with the existing PPIE representatives aimed to introduce the project and the research design, following the sandpit workshops. Feedback on the project and acceptability of the research has been positive. The consensus is that the research questions are clear, and users will understand why it is being conducted. Feedback on the research design has been positive. The group are supportive of the methodology and have provided useful insight on assumptions of Facebook page use (frequency and level of engagement of users), recruitment, sampling and ethics in analysing digital content among others.

Future involvement will include A) research tools to ensure (lay) language, flow, accessibility and overall suitability for the target audience, B) critically discuss emerging findings, further analysis that can add to the evidence and related implications of findings. Depending on requirement, this can happen at subsequent stages of the analysis, C) reporting stage for lay summaries and implication of findings, D) dissemination in terms of i) ensuring content is appropriate for both the medium of dissemination and targeted audience, ii) dissemination plan and iii) possible engagement at dissemination stage by way of presenting findings or participation in events, videos etc. This will depend on their availability and willingness to participate.

Future involvement will create opportunities to receive and provide feedback and recognition on their collaboration with the project team, and the impact of their involvement with the project.

Data protection and patient confidentiality

Where data is collected on third party data collection platforms outside of LSBU (e.g. Qualtrics) data will be anonymised at the point of download, and the third party copy of the data deleted. All data will be kept in an anonymous or pseudo anonymous format and stored on LSBU secure servers. Any key files will be kept on a secure server, encrypted and passwords shared separately from files. Data may be stored indefinitely with participant consent.

Where data is offered to online repositories (see *Dissemination*, below), it will be rendered fully anonymous prior to upload.

When audio files are transcribed, transcripts will be pseudoanonymised. All information which is collected during the course of the research will be kept confidential by using password protected computerised records. All written transcripts will be kept in a secured locked filing cabinet, when not in use. Any information regarding participants that is shared with others (for instance in reports, publications or shared with a supervisor) will also have pseudonyms used, which will prevent the identification of people involved in the study. All data will be secured in a locked filing cabinet for as long as required for the duration of the study and will then be destroyed 18 months after the completion of the project.

Indemnity

Indemnity will be provided by LSBU for the research activity undertaken by its staff.

Dissemination and output plans

LSBU will own foreground IP arising from the project, including the final dataset(s) and transcripts. Data will be made available as a 'public good' for secondary analysis (see below). Details of IP ownership and usage rights will be finalised in the collaboration agreement between LSBU and ECAS.

Key research outputs will include:

- 1) Interim report of findings
- 2) A final report for the ECAS team (also lodged on OSF)
- 3) Peer review journal articles (also lodged on OSF)

We will also offer a workshop event in which the study findings are presented to ECAS, and other meetings on an ad-hoc basis as required.

The final dataset(s) will be lodged (in fully anonymous form) on an Open Science Framework site which will also host study documentation, analysis files (syntax, coding frames, etc.) and research outputs associated with the project.

NB The above applies to quantitative work packages only. Qualitative datasets (including interview transcripts and Facebook posts and comments) will not be lodged on an Open Science Framework due to the nature of the data, it may not be possible to fully anonymise these data. In this case, in compliance with the General Data Protection Regulation, data will be kept for 10 years from study completion and will then be destroyed.

Milestones

Stage	Activity	Completion Date
Inception	Introductory meetings	Jan 2021
	Identification of project team	Feb 2021
	Identification of local stakeholder group	Jan/Feb 2021
	Sandpit workshop 1 - understanding the intervention	25 th Feb 2021
	Sandpit workshop 2 - understanding the theory of change	18 th March 2021
	Sandpit workshop 3 - agreeing a design	30 th March 2021
	Sandpit evaluation survey	March 2021
	Evidence scoping	Feb 2021
	Design and protocol development	March/April 2021
	Ethics application	June 2021
	Research Governance Approval	N/A
	Research Registration	April 2021
	Local PPIE recruitment	Feb-March 2021
	Local collaboration agreement	May 2021
Implementation Quantitative Work Package	Primary Analysis Sample - Data collection platform preparation	July 2021
	Primary Analysis Sample - Ad collateral preparation	June 2021
	Primary Analysis Sample - Online marketing admin	Nov 2021
	Primary Analysis Sample - Liaison with recruitment panel inc. admin	TBC
	Primary Analysis Sample - Data collection	Nov 2021
	Primary Analysis Sample - Data screening / preparation	Nov 2021
	Primary Analysis Sample - Analysis	Dec 2021
	Primary Analysis Sample - Data archiving	Jan 2022
	Social Network Analysis – Data harvesting	Aug 2021
	Social Network Analysis - Data screening / fidelity checks / preparation	Aug 2021
	Social Network Analysis - Analysis	Sept 2021
	Social Network Analysis - Data archiving	October 2021
Implementation Qualitative work package	Facebook discourse analysis - Data harvesting	Sept 2021
	Facebook discourse analysis - Initial coding and development of a coding framework	Oct 2021
	Facebook discourse analysis - Main data analysis	Dec 2021
	Qualitative Interviews - Development of interview schedule	May 2021
	Qualitative Interviews - Recruitment of participants	June 2021
	Qualitative Interviews - Data collection	Sept 2021
	Qualitative Interviews - Data analysis	Nov 2021
Implementation Health economic work package	Scoping: Identify and request data needed from stakeholders (e.g. specific finance data)	Sept 2021
	Data received from stakeholders	Nov 2021
	Analysis: Health economic completed	Jan 2022
Project Management and Reporting	Reporting to stakeholder group	Ongoing - TBC
	PPIE meetings	Ongoing - TBC
	Project management meetings	Every six weeks
	Primary Analysis Sample – interim reporting	Dec 2021
	Social Network Analysis – interim reporting	Oct 2020
	Discourse Analysis – interim reporting	Dec 2021
	Qualitative Interviews – interim reporting	Dec 2021
	Final reporting	Mar 2022

References

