Effects of ECAS and underlying processes: For those that have joined ECAS, we will test how engagement with the ECAS Facebook page and group relates to (i) a sense of social connection and (ii) how both engagement and the sense of social connection relate to the interim outcomes of increased health literacy, covid protective behaviour and community champion activity (see Figure 2). A further analysis will compare levels of each of these factors amongst those who did engage with the intervention versus a comparator group who did not and across socio-demographic groups if the data allows (i.e., using moderation analyses). Amongst both samples, we will also measure current levels of mental health and test relationships between these and each factor. These analyses will provide a quantitative evaluation of the extent to which the intervention met its aim to ‘inform’, ‘prevent’ and ‘assist’. Additionally, for those who engage in it, it will also identify which interim outcomes were most impacted and the extent to which this effect was mediated by social connection.

[figure not shown]

Figure 2: Primary conceptual model to be tested.

Given the nature of the study, much of these data will be retrospective (i.e., people’s recollection of their behaviours). In these instances, we will ask participants to recall how they felt during what our preparatory work with stakeholders (stakeholder workshops and also a PPIE workshop), identified as a *critical phase* of the intervention’s deployment. The critical phase selected for the quantitative analysis of new data is the the first two weeks following the lifting of the first lockdown.

Table 1 (see below) indicates broad operationalisations of each of the factors, the source of data (and whether it is current or retrospective) and possible measurement instruments.

Table 1: Indicative primary outcome measures¹

Factor	Operationalisation(s)	Source of data	Indicative instrument
Interaction with ECAS	Did / did not engage with site Intensity of engagement (users only)	Facebook data or self-report	Study generated scale/metrics
Social connection	Sense of social connection with others Collective responsibility	Self-report (current) Self-report (critical phase)	Validated scale (Lee, Draper & Lee, 2001)
Health literacy	Level of perceived digital health literacy	Self-report (current)	Use of two subscales: information searching and evaluating reliability from validated scale (Van der Vaart & Drossaert, 2017)

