COVID protective behaviours	Engage in behaviours which are likely to reduce infection risk to self and others	Self-report (critical phase)	Items from Freeman et al. (2020)
Community champion activity	Helped others practically in real world Signposted to online reliable information Corrected misinformation online	Self-report (critical phase)	Study generated scale
Mental health	Level of anxiety Satisfaction with life COVID specific anxiety syndrome	Self-report (critical phase)	GAD-7 (7 items) PHQ-9 (9 items) SWLS (~5 items) Nikčević & Spada (2020)
	Level of anxiety	Self-report (current state)	GAD-7 (7 items)

¹ Use of tools is subject to securing permissions, where required, from authors.

The relationships highlighted in Figure 2 will be analysed using the Hayes PROCESS macro tool (Hayes, 2018), focusing on one effect and mediation per model (see power analysis below for a rationale).

This aspect of the research will also take additional *secondary outcome measures* from those who engaged with ECAS including *sense of ownership of the site* (self, community, local authority), *understandings of information provenance*, *confidence in information*, *frequency of referrals made to the site* and *reliance upon site*. This will allow exploratory testing of how these factors relate to the efficacy of the intervention. These will need to be short measures (i.e., single item scales) given the length of the primary outcome measures and subsequent possible impact upon participant attrition.

Analysis of existing data

Social network analysis: We will explore the feasibility of using social network analysis (SNA) to see the extent to which influence (categorised as interactions) in the network is central (via admins out to members) or distributed (member to members, including core member and peripheral members) over a given time period (see *Sampling*, below). Data will be analysed using the SNA package on R.

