Work Package 1: We will aim to recruit a sample of $n = 225$ people who have signed up to the ECAS Facebook page and group. We will also recruit a comparative, equally sized sample of Facebook users who did not sign up to the page nor recall being exposed to it. These will be either a comparative demographic profile, or we will weight responses to match our samples. Recruitment will be conducted via Facebook. The total target sample size will be $n = 450$. See *Recruitment*, below, for details on how these samples will be secured.

Inclusion criteria:

- 18+ years of age
- Facebook user
- Enrolled in ECAS page and group on Facebook (ECAS condition only)
- Works or lived in Essex during first lockdown period

Exclusion criteria:

- Enrolled in ECAS page and group on Facebook (comparator condition only)
- Unable to give informed consent

Social network analysis: Data will be collected from the ECAS group page drawing on posts made (i) during the first two weeks of the first lockdown and (ii) the first two weeks following the lifting of the first lockdown. In each period, the highest day traffic will be selected, then the lowest (non-contiguous) day and then the non-contiguous day closest to the mean. We will manually sample and code 800 contiguous interactions per day, three days per phase (total $n = 2400$ interactions).

Size of sample

Primary analysis sample: Our within condition sample of $n = 225$ allows detection of single mediation effects at power = 0.81 assuming medium (Pearson $r = .30$) relationships between variables (calculated using 'pwr2ppl' R package 'med' function). In the absence of suitable pilot data, these levels of relationship have been selected as they represent effects which are likely, and are in line with relationships between social identity and efficacy and behaviour observed in other studies (i.e., Frings, Wood & Albery, in press). Relationships smaller than that powered for are also likely to be of less practical significance. A sample sufficient to power multiple mediation models is beyond the scope of the current study.

Social network analysis: This sample size indicated above balances a manageable amount of data inputting and sufficient data to generate meaningful insight. Focusing on high and low traffic days gives a representation of time the group is seeking and receiving information from the centre of the network and times when they are engaged in more general interaction.

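### The protocol promises to identify the most impacted interim outcomes, but its one-effect-per-model analysis gives no estimate or interval for differences between outcomes

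*Protocol*

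**What the plan says.** The section Primary analyses of new data (Work Package 1) relates engagement with ECAS, and the sense of social connection, to three "interim outcomes of increased health literacy, covid protective behaviour and community champion activity". It then states that, for those who engage, "it will also identify which interim outcomes were most impacted", together with how far social connection mediated the effect. The commitment carries no condition.

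The text after Table 1 in the same section fixes the analysis: the Hayes PROCESS macro, "focusing on one effect and mediation per model", with a pointer to the power analysis for the reason.

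Under Size of sample, the 225 ECAS users are justified because that number "allows detection of single mediation effects at power = 0.81", "assuming medium (Pearson $r = .30$) relationships between variables". The same paragraph puts power for multiple mediation models out of scope.

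Table 1 measures the three outcomes differently. Health literacy is a current self-report on two subscales of a validated instrument. Protective behaviour is recalled from the critical phase, with items taken from a published study. Champion activity is recalled from the same phase on a scale built for this study.

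**The concern.** Saying that one outcome was more affected than another is a statement about a difference. Three models fitted one outcome at a time give three effects, each with its own interval, and nothing on the differences between them. The reader is left to compare point estimates, or to compare which tests reached significance. Either comparison can produce an apparent leader when the true effects are the same. The outcomes are also on different scales, so raw coefficients cannot be set side by side.

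At stake is a named result of the primary analysis: which of the interim outcomes ECAS engagement is said to have moved most.

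**Working it through.** **Inputs.** From the protocol: n = 225 users, three interim outcomes, planning correlation .30 for every relationship, stated power 0.81. Assumed, because the protocol does not give them: two-sided alpha 0.05, and a correlation r₁₂ between outcomes of .3 to .5 (wider range .1 to .7 where shown).

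**Step 1: the protocol's own figure.** Sobel power for a single mediation, all r = .30:
- a = .30; b = (.30 − .30 × .30)/(1 − .09) = .21/.91 = .2308; indirect effect ab = .0692
- R² = (.09 + .09 − 2 × .027)/.91 = .1385
- SE_a = √(.91/223) = .0639; SE_b = √(.8615/(.91 × 222)) = .0653
- z = ab/√(a²SE_b² + b²SE_a²) = 2.824; power = Φ(2.824 − 1.960) = 0.806

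This reproduces 0.81. It is power for one effect in one model and says nothing about a contrast between outcomes.

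**Step 2: precision of a difference.** For two correlations with engagement, r₁ and r₂, in the same people:
- c = r₁₂(1 − r₁² − r₂²) − ½r₁r₂(1 − r₁² − r₂² − r₁₂²)
- SE = √{[(1 − r₁²)² + (1 − r₂²)² − 2c]/n}

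Example with r₁ = r₂ = .30 and r₁₂ = .3: c = .2460 − .0329 = .2131; SE = √[(1.6562 − .4263)/225] = .0739; 95% half-width 1.96 × .0739 = .145. With r₁₂ = .5, SE = .0628 and the half-width is .123.

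**Step 3: no true difference.** Simulation (10,000 samples, n = 225, all r = .30):
- Each outcome ranks first in about 33% of samples.
- The highest and lowest observed correlations differ on average by 0.089 (r₁₂ = .3) or 0.075 (r₁₂ = .5).
- Exactly one or two of the three Sobel tests are significant in 4.0% + 19.9% = 23.9% (r₁₂ = .3) or 5.1% + 14.9% = 20.0% (r₁₂ = .5) of samples. The simulated rate for a single test was about 0.89, above the formula value in Step 1.

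**Step 4: one outcome truly stronger, other two at .30.** Share of samples in which the right outcome ranks first on the engagement correlation:

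| True r of strongest | r₁₂ = .3 | r₁₂ = .5 |
|---|---|---|
| .35 | 62% | 67% |
| .40 | 86% | 90–91% |
| .50 | over 99% | over 99% |

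**Step 5: power of a formal comparison, .40 against .30.**
- r₁₂ = .3: SE = .0719; Φ(.10/.0719 − 1.96) = 0.285
- r₁₂ = .5: SE = .0612; Φ(.10/.0612 − 1.96) = 0.372
- Over r₁₂ = .1 to .7, power runs from 0.24 to 0.55. The difference detectable with 80% power falls from about 0.22 to 0.13 (0.20 at r₁₂ = .3, 0.17 at .5).
- Bonferroni for three pairs (critical value 2.394) gives Φ(1.391 − 2.394) = 0.16 at r₁₂ = .3 and Φ(1.633 − 2.394) = 0.22 at r₁₂ = .5.

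**Step 6: measurement.** If outcome reliability were 0.9 for one scale and 0.6 for another (illustrative values), a true .30 would appear as .30 × √.9 = .28 and .30 × √.6 = .23. Standardising does not remove that gap.

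**The case against.** A reader might infer that separate models cannot support a ranking at all, or that any ranking would be mostly noise. The documents do not support that. All three outcomes come from the same participants, so effects from separate models can be compared by joint resampling or a dependent-correlation test. Step 4 shows that a gap of 0.10 is ordered correctly most of the time, and a gap of 0.20 nearly always. The r = .30 is a planning value for sample size, not a forecast that the three effects are equal. This part of the objection stands, and it limits the point to effects that are equal or close.

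Three further limits also stand:
- The sentence is about the effect of engagement first and mediation second. The engagement correlations are therefore the relevant figures for a ranking, and indirect effects come second.
- It might be inferred that this ordering would steer roll-out elsewhere, or that it is the protocol's answer on informing, preventing and assisting. The protocol links deployment in other regions to learning from the evaluation as a whole (Project aim). It ties the three service aims to the analyses described just before this sentence.
- The wording is plural and sets no rule for ordering, so a descriptive report of effects with intervals could be consistent with it.

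The last argument is that standardisation and pairwise intervals belong in a SAP that is not shown. A SAP could supply them. But the protocol itself states the conclusion without condition, fixes the modelling approach, and sizes the sample for something else. The mismatch lies in what is written, not only in what is left out.

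**Conclusion.** The point holds in a limited form. The protocol commits to identifying the most impacted outcomes, and its stated models produce no between-outcome estimate or interval. The sample is sized for one mediation effect only. Where true effects are equal or close, the outcome named is largely chance: an observed spread in correlations of about 0.08 to 0.09 arises with no true difference, and 20 to 24% of studies show a mixed pattern of significance. Gaps of about 0.10 in r are usually ordered correctly (86 to 91%) but would seldom be confirmed formally (power 0.29 to 0.37 before any allowance for three comparisons).

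These figures assume two-sided alpha 0.05, multivariate normal data and an outcome intercorrelation of .3 to .5, none of which the protocol states. They do not show that a ranking is impossible, only that the stated analysis supplies no measure of how far to trust one. This should be corrected, and it does not undermine the single-outcome analyses.

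**What to change.** Standardise the three interim outcomes. Estimate the engagement (total) effects, and secondarily the indirect effects, on common bootstrap resamples of the same participants. Report intervals for the three pairwise differences, with allowance for three comparisons. The one-effect-per-model structure can stay.

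Describe an outcome as most impacted only where those intervals support it. State alongside it that instruments and recall periods differ (current validated subscales, recalled items, a study-built recall scale), so a difference may reflect measurement rather than impact. Otherwise, report the standardised effects with their intervals descriptively and say that the outcomes cannot be ranked. The sentence in Primary analyses of new data should be reworded to match.

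The cost is a little extra analysis on data already planned, with no new participants. The drawback is that at n = 225 the conclusion will often be that the outcomes are not distinguishable.

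### Table 1 gives social connection mixed time frames, and the named mediator appears to be measured over a year after two of the three outcomes it is meant to explain

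*Protocol*

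**What the plan says.** The Protocol, under 'Primary analyses of new data', makes social connection the link between engagement and three interim outcomes: health literacy, COVID protective behaviour and community champion activity. For ECAS members it undertakes to report "the extent to which this effect was mediated by social connection". Each relationship goes into a single-mediator PROCESS model, and the 'Size of sample' section justifies n = 225 on that test. The text introduces Table 1 as showing, for each factor, whether the data are current or retrospective.

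Table 1 then gives:

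- **Social connection (mediator):** two components, "Sense of social connection with others Collective responsibility", set against two labels, "Self-report (current) Self-report (critical phase".
- **Health literacy:** "Level of perceived digital health literacy Self-report (current".
- **COVID protective behaviours:** "Engage in behaviours which are likely to reduce infection risk to self and others Self-report (critical phase".
- **Community champion activity:** also critical phase.
- **Interaction with ECAS (exposure):** Facebook data or self-report, with no period stated.

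The critical phase is the fortnight after the first lockdown ended. The Milestones table completes data collection for this sample in November 2021.

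**The concern.** A mediation model assumes that engagement acts on connection and that connection then acts on the outcome. If connection is scored as it stands in 2021 and the behaviour as it was in 2020, the arrow from mediator to outcome points back in time. There is an obvious alternative: people who helped neighbours or took precautions in 2020 may feel more connected afterwards. PROCESS would show that path as an indirect effect through connection, and nothing in the protocol would reveal the difference.

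The extent of mediation by connection is one of the stated products of Work Package 1. The recall stem is fixed once the survey is fielded, so no later analysis plan can repair it.

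**Working it through.** **1. Pairing the components with the labels.** The social-connection row has two components and two labels. Taken in order, sense of connection is current and collective responsibility is critical phase. The mental-health rows support this reading. One label there covers several scales, and a measure taken a second time (GAD-7) gets its own line. The alternative, both components at both times, cannot be excluded, because the cell lines are lost in the text available here.

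**2. Time order in each model, on the line-by-line reading.**

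| Outcome | Mediator (sense of connection) | Outcome period | Order |
|---|---|---|---|
| Health literacy | current | current | same time |
| Protective behaviours | current | critical phase | mediator later |
| Champion activity | current | critical phase | mediator later |

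**3. The gap.** No calendar date is given for the end of the first lockdown. Table 2, written for Work Package 2, places the following interim in July/August 2020. From there to November 2021 is 15 to 16 months. November is a completion date, and platform preparation is due in July 2021, so the earliest responses could come about a year after the critical phase. Over a year by completion is what the document supports.

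**4. The plan's own power figure.** Inputs from 'Size of sample': n = 225 and all correlations .30. Two-sided alpha of 0.05 is assumed.

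- a = .30
- b = (.30 − .30 × .30)/(1 − .30²) = .21/.91 = .2308
- R² = 2 × .30 × .2308 = .1385
- SE(a) = √(.91/223) = .0639
- SE(b) = √(.8615/(.91 × 222)) = .0653
- Sobel z = ab/√(a²·SE(b)² + b²·SE(a)²) = 2.82
- Power = Φ(2.82 − 1.96) = 0.806

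Using n as the divisor in both standard errors gives 0.811. The stated 0.81 is reproduced. It depends only on correlations, so it is the same whichever of mediator and outcome came first.

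**5. What a reverse path would do (illustration).** Model with standardised variables:

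- connection in 2020 = .3 × engagement + error
- behaviour in 2020 = .3 × engagement + error, with no effect of connection
- connection in 2021 = .5 × connection in 2020 + g × behaviour in 2020 + error

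The planned regressions then use 2021 connection as mediator (n = 225, 4,000 runs). True mediation is zero throughout.

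| g (assumed) | Sobel | Joint significance |
|---|---|---|
| 0.1 | 11% | 24% |
| 0.2 | 54% | 73% |
| 0.3 | 92% | 96% |

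Repeat runs agree to within about two percentage points. With g = 0 both tests stay below 5%. The stability of .5 and the values of g are assumptions, not protocol figures.

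**6. Does aligning the period cure it?** Raising stability to .9, so that the score nearly equals 2020 connection, while keeping the same reverse path gives about 32%, 87% and 100% by joint significance. The false positives come from the reverse path, not from the label alone. Aligned recall removes a reversal built into the design, but it does not establish order.

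**The case against.** The strongest reply is that the table is ambiguous rather than wrong. A reader might infer that the whole mediation analysis runs backwards. The documents do not support that. The same cell carries a critical-phase component, and a model using it would not be reversed. The health-literacy model is current on current. Table 1 is headed as indicative, and no section says which component enters which model. All of this stands, and it limits the point to two models on the natural reading. It does not remove the point, because the text names sense of connection as the mediator and no other section gives that scale a critical-phase measurement.

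A reader might also take 15 to 16 months as a fixed gap. It rests on a Work Package 2 sampling table that prints the same July/August 2020 dates for two different interim periods, and on a completion date.

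A reader might further see a contradiction on mental health, since the text says "Amongst both samples, we will also measure current levels of mental health and test relationships between these and each factor" while most of the scales in Table 1 are for the critical phase. That does not hold. Table 1 has a separate row for current anxiety by GAD-7, and measuring other scales for the critical phase conflicts with nothing.

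Finally, the simulated rates depend on assumed paths and on the test chosen. At g = 0.1 the Sobel rate is less than half the joint-significance rate. The percentages show what could happen, not what will.

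**Conclusion.** The point holds in limited form. On the line-by-line reading of Table 1, the named mediator is current while protective behaviours and champion activity are recalled from the critical phase. In those two of the three models the mediator is measured over a year after the outcome, and a significant indirect effect could equally reflect behaviour raising later connection. On any reading, the protocol does not say which component and time frame enter each model.

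The conclusion rests on the pairing of components and labels in one table row and on the dates inferred in the working. The stated sample size and power are not in error. The size of any false-positive risk is unknown: the simulated 11–24%, 54–73% and 92–96% hold only for the assumed reverse effects of 0.1, 0.2 and 0.3 with stability .5.

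**What to change.** Before the survey is fielded:

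1. In Table 1, put each component of social connection on its own line with its own time frame, and also take the sense-of-connection scale with the critical-phase stem.
2. State that critical-phase connection (and critical-phase collective responsibility) is the mediator in the protective-behaviour and champion-activity models. Use current connection for health literacy, or as a sensitivity analysis.
3. State the period to which the engagement measure refers, since Table 1 gives none.
4. Report the indirect effects as cross-sectional associations consistent with mediation, and soften the promise to show how far the effect was mediated. Recalling both variables in one sitting does not establish time order.

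The cost is a table edit and one repeated scale in a survey that the protocol already regards as long. The validated connection scale would be used in a recall version, which may affect its validity and may need the author permission that the Table 1 footnote mentions. The sample size does not change.
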